## STUDY SUMMARY

Title	NOVEMBER (Novem- (9), BrEast Radiation), A Phase II trial of a 9 day course of whole breast radiotherapy for early stage breast cancer.
Short Title	NOVEMBER.
Protocol Number	IRB#103976
IND	N/A
Phase	Phase II
Design	Single arm non-inferiority trial
Study Duration	8 years (3 years enrollment, 5 years follow-up)
Study Center(s)	Single-center at Huntsman Cancer Institute
Objectives	
Primary objective will be to evaluate 24 month breast photographic cosmetic scores with 9 fraction hypofractionated radiation compared to published hypofractionation radiation.
 
Secondary objectives include evaluation of patient reported outcomes, radiation toxicities, disease recurrence, and cost effectiveness.

Number of Subjects	102 enrolled for at least 87 evaluable
Diagnosis and Main Eligibility Criteria	Stage 0-IIIB breast cancer in the setting of breast conservation. Exclusion: Prior RT, Recurrent setting, Node positive, NO chemo before RT, No pregnancy
Study Product, Dose, Route, Regimen	External Beam Radiation Therapy (EBRT)
Duration of administration	9 days of Radiation (11-14 calendar days)
Reference therapy	Study therapy will be compared with published phase III data on 15 day, & 16 day hypofractionation breast RT studies from the UK and Canada.
Statistical Methodology	The primary analysis will be a one sample t-test. The null hypothesis will be that the true rate is good to excellent photographic breast cosmetic assessment in $\leq 70\%$ of patients. The one sided alternative hypothesis is a good to excellent photographic breast cosmetic assessment in $> 70\%$ of patients. Assuming the true rate is 80% (e.g. exact equivalence), a sample of 87 evaluable subjects will provide 80% power at the alpha = 0.1 significance level.

[figure not shown]
Protocol name: NOVEMBER (Novem- (9), BrEast Radiation), A Phase II trial of a 9 day course of whole breast radiotherapy for

early stage breast cancer.

Version Date: 23NOV2021

Principal Investigator: [name]

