## 2.6 Cost Effectiveness

We hypothesize that a 9 fraction course will be more cost effective. Costs will be compared to 45 de-identified patients that were treated with a standard hypofractionated regimen of 19 treatments. Direct costs of medical care to each patient will be estimated using utilization information from HCI financial/claims data. Generalized linear models will then be used to model these costs as a function of treatment, time on study, and all available baseline patient characteristics to assess the extent to which estimated direct cost is impacted by the type of radiation dosing. Given the well-known fact that healthcare costs are typically highly skewed, regression models will employ the appropriate distribution and transformation link.

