11. Clinical assessments above are a minimum for trial purposes only and do not represent the entirety of necessary medical care. Weekly treatment visits occur once every 5 treatment fractions during radiation. Follow up visits should be scheduled per standard of care and physician discretion. Per NCCN guidelines, clinical follow up visit should occur 1-4 times per year with continued annual mammograms.
12. Identified patients who voluntarily agree to complete the Health Care Expense Survey should be provided this survey at 2-8 weeks post standard of care hypofractionated radiation. (See section 8.4 Economic Analysis for further instruction)
13. Patients who volunteer to complete the Health Care Expense Survey must be provided with the Informed Consent Letter prior to completing the questionnaire.

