## 8.4 Economic Analysis

A reduction in number of radiation treatments and thereby number of visits to the radiation therapy department will benefit patients directly, both in terms of reduced direct and indirect healthcare costs. Direct healthcare costs are expected to go down because of an expected reduction in health care utilizations services (e.g., office visits, emergency room visits, inpatient admissions). With short-course treatment patients may be able to take less time off from work and/or return to work faster. Potential improvements in cosmetic-outcomes and side effects of radiation therapy with short-course therapy could also translate into a reduction in utilization of health care services, further enhancing the economic impact of hypofractionation. Indirect costs are also expected to be lower for the intervention arm because patients in this arm are expected to resume normal activities sooner. This in turn would help save family caregiver time as well as the cost of dependent care, which will further add to the saving in indirect costs. Therefore, robust measurement of the patient resources used to receive radiation therapy and utilization of health services is a critical component of this trial.

Patients will be given a diary with question domains to be filled out weekly during radiation therapy in order to help improve recall (Appendix II, III and IV).

We will utilize available CPT code charges generated from the time of registration to 2-8 weeks after the completion of radiation therapy. We will utilize the HCI financial data to estimate reimbursable charges.

Questions are adapted from the Medical Expenditure Panel Survey-Household Component (MEPS-HC) created by

AHRQ ([https://meps.ahrq.gov/survey\\_comp/hc\\_survey/2014/DD111214.pdf](https://meps.ahrq.gov/survey_comp/hc_survey/2014/DD111214.pdf)).

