## **10 REGISTRATION GUIDELINES**

**Patients must meet all of the eligibility requirements listed in Section 4 prior to registration.**

**Study related screening procedures can only begin once the patient has signed a consent form. Patients must not begin protocol treatment prior to registration.**

Treatment should start within five working days after registration.

To register eligible patients on study, complete a Clinical Trials Office Patient Registration Form and submit to: [[contact]](mailto:[contact]).

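### The direct-cost model adjusts for time on study, which is undefined, has no start date for the comparators and, under the section 8.4 charge window, is partly a consequence of the schedule being costed

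*Combined protocol and SAP*

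**What the plan says.** Section 2.6 (Cost Effectiveness) hypothesises that nine fractions will be more cost effective. It states that "Costs will be compared to 45 de-identified patients that were treated with a standard hypofractionated regimen of 19 treatments". Direct cost is to be estimated from institutional financial and claims data. Generalized linear models will then "model these costs as a function of treatment, time on study, and all available baseline patient characteristics", and their stated purpose is "to assess the extent to which estimated direct cost is impacted by the type of radiation dosing".

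Section 8.4 (Economic Analysis) gives the only charge window: "We will utilize available CPT code charges generated from the time of registration to 2-8 weeks after the completion of radiation therapy". It describes the 45 comparison patients as people on standard hypofractionated radiation who are ineligible for the protocol or do not wish to join it. Their stated contact is one survey. Study Calendar footnote 12 says that they "should be provided this survey at 2-8 weeks post standard of care hypofractionated radiation", and footnote 13 adds a consent letter beforehand.

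Section 10 applies to trial patients: "Treatment should start within five working days after registration". Section 3.4 gives three years of clinical follow-up and a chart review at five years. Section 9.2.4 speaks of costs measured over multiple years and discounted at 3.5%, includes the cost of treating side effects, and builds the ICER from mean differences. It mentions neither the generalized linear model nor time on study.

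**The concern.** A model meant to show what the schedule does to cost should not hold constant something that the schedule itself changes. If time on study is the section 8.4 window, the length of the radiation course is one of its components. Charges that arise because treatment lasts longer would then be credited to time and not to the regimen. Section 8.4 expects direct costs to fall through fewer office visits, emergency visits and admissions. Any of that use which builds up with calendar days is what the covariate would absorb.

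There is also a plain definitional gap. The section 8.4 clock starts at registration, the comparators are outside enrolment, and no substitute date is named for them. As written, the covariate cannot be computed for one of the two groups. Cost is a named secondary objective (1.2.4), so the estimate will be reported and interpreted.

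**Working it through.** The plan states no effect size, variance or power for this model, so there is no figure to reproduce. The check asks how far the schedule moves the covariate, and what adjustment then does.

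**1. Treatment span.** Assume five fractions a week and count calendar days for Monday to Friday starts.
- 9 fractions: 11, 11, 13, 13, 13 days, mean 12.2 (the Study Summary gives 11-14).
- 19 fractions: 25, 25, 27, 27, 27 days, mean 26.2.
- Difference: 26.2 − 12.2 = 14 days.

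**2. How much of the covariate the schedule explains.** Take time on study as lag + span + close. The lag is uniform on 1-7 days (section 10), and the close is uniform on 14-56 days (section 8.4). The comparators are assumed to have a date equivalent to registration.
- Within-group variance: (7² − 1)/12 + 0.96 + 42²/12 = 4 + 0.96 + 147 = 152.
- Between-group variance, 102 trial patients and 45 comparators: (102/147) × (45/147) × 14² = 41.6.
- R² = 41.6/(41.6 + 152) = 0.21. Simulation gave about 0.22.

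The schedule therefore determines the covariate only in part, and the 42-day spread of the close dominates. If the close were nearly constant (SD 1 day), R² in simulation is about 0.88 and the standard error of the treatment coefficient roughly doubles.

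**3. Effect on the estimated saving, under assumed costs.** Let cost = 1 unit per fraction + g units per calendar day in the window. The total difference is 10 + 14g. Adjustment leaves about 10. The share removed is 14g/(10 + 14g). Gamma model simulation (300 replicates, 102 vs 45):

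| g | 14g/(10 + 14g) | Unadjusted, identity link | Adjusted, identity link | Share removed, identity link | Share removed, log link |
|---|---|---|---|---|---|
| 0 | 0% | −10.0 | −10.0 | 0% | 0% |
| 0.02 | 2.7% | −10.3 | −10.0 | 2.7% | 3.4% |
| 0.05 | 6.5% | −10.7 | −10.1 | 6.2% | 7.7% |
| 0.1 | 12.3% | −11.5 | −10.1 | 12.1% | 13.8% |
| 0.2 | 21.9% | −12.8 | −10.0 | 21.9% | 24.9% |

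On the identity scale, the part of the saving tied to the ten fewer fractions stays in the treatment coefficient throughout.

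**4. Daily cost only after radiation.** Within each group, time on study varies mainly through the close, so the time slope is learned mostly from days after treatment and then applied to the 14-day treatment gap. If b units per day accrue only after radiation, the true saving is 10. The linear slope is b × 147/152 = 0.967b, and the adjusted saving is 10 − 14 × 0.967b = 10 − 13.5b. That is 9.3 at b = 0.05, 8.6 at 0.1 and 7.3 at 0.2. Here adjustment takes the estimate below even the per-fraction saving.

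**5. The other reading.** If time on study means follow-up (sections 3.4 and 9.2.4), trial patients have years of it and comparators have one survey contact at 2-8 weeks. The two ranges barely overlap. The term is then close to a relabelling of treatment group, and separating their effects rests on extrapolation.

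**The case against.** The strongest reply is that section 8.4 never uses the term time on study, so equating it with the charge window is an interpretation. That stands, and it is why the point is put under two readings. It does not rescue the model, because the follow-up reading replaces conditioning on a consequence of treatment with near-collinearity.

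A reader might infer that the covariate is simply fixed by the number of fractions. The documents do not support that: even under the section 8.4 window, the schedule explains only about a fifth of its variance. A reader might also infer that the model will understate the saving by a known percentage. It cannot be known, because the documents give no cost per fraction or per day. Section 8.4 ties the benefit first to fewer treatments and visits, and weekly treatment visits occur once every five fractions. Costs of that kind follow fractions and are not lost. Nor does section 2.6 say that time enters as an exposure offset. It is listed as an ordinary model term, so conclusions about a cost-per-day model do not apply.

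There are legitimate reasons to think about time. Section 5.5 provides for withdrawal, loss to follow-up and death, the close varies between patients, and section 9.2.4 contemplates several years of cost. These call for explicit handling of unequal observation, which an undefined regression term does not give. One caveat also stands: background charges that would arise under any schedule are not a saving, even though they too accrue by day.

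Finally, the sentence sits in the background section and the analysis is secondary. This limits the weight of the point, but 2.6 is the only place where a model for direct cost is specified.

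**Conclusion.** The concern holds in a limited form. Time on study is undefined and cannot be computed for the comparators as written. Under the section 8.4 window it is partly determined by fraction number, by about 14 days, so adjusting for it can remove any part of the saving that accrues with calendar time. Under the follow-up reading it is nearly collinear with treatment group. Neither reading makes the stated model a sound estimate of the effect of the schedule on direct cost.

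The 14 days rests on five fractions a week. The percentages are illustrations under assumed costs: 0% if nothing accrues per day anywhere in the window, and 22-25% if each day costs 0.2 of a fraction. The primary cosmetic endpoint is unaffected. The change is worth making before costs are extracted.

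**What to change.** In section 2.6, delete time on study from the covariates. For the direct-cost comparison:
- Name one index date that exists in both groups, such as the planning CT or the first fraction.
- Name one fixed close, such as day 56 after the last fraction.
- Treat observation cut short by withdrawal, loss to follow-up or death as a censoring problem, with the rule stated.

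A close counted from the last fraction leaves comparators with about 14 more days of charges. That keeps schedule-related cost in the comparison, but it also counts background care. A sensitivity analysis closing on the same day after the first fraction in both groups would show how much this matters; 27 + 56 = 83 days covers the longest 19-fraction course counted above.

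Reconcile the window in 8.4 with the multi-year and side-effect costs in 9.2.4, and state there whether the adjusted model difference or another mean difference feeds the ICER.

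The cost is mainly wording, since charges come from institutional records. Extraction must wait until day 56 for every patient. The sponsor must also confirm that treatment and charge dates can be retrieved for the comparators, whom 2.6 describes as de-identified.

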## 3 STUDY DESIGN

### 3.1 Description

This will be a phase II single arm non-inferiority trial. Trial patients will receive 9 fractions hypofractionated radiation. Patients will be evaluated for breast photographic cosmetic scores with hypofractionated radiation compared to standard fractionation 24 months after radiation. Secondary objectives include evaluation of toxicities, recurrence, patient reported outcomes and cost effectiveness.

Protocol name: NOVEMBER (Novem- (9), BrEast Radiation), A Phase II trial of a 9 day course of whole breast radiotherapy for early stage breast cancer.

Version Date: 23NOV2021

Principal Investigator: [name]

### **3.2 Number of Patients**

87 Analyzable patients. Plan for 15% drop out rate, therefore plan to enroll 102 patients

### **3.3 Number of Study Centers**

At this time, Huntsman Cancer Hospital is the only planned enrolling institution.

### **3.4 Study Duration**

We anticipate enrolling 30 patients per year on this trial with 3 years of clinical follow up. We plan to do a chart review at 5 years for any long-term toxicities or evidence of late breast cancer recurrences.

## 4 ELIGIBILITY CRITERIA

This eligibility checklist is used to determine patient eligibility and filed with enrolling investigators signature in the patient research chart.

**Patient No.** \_\_\_\_\_

**Patient's Initials: (L, F, M)** \_\_\_\_\_

### 4.1 Inclusion Criteria

**Yes/No (Response of "no" = patient ineligible)**

4.1.1 \_\_\_\_\_ Histologically confirmed invasive carcinoma and/or Ductal Carcinoma In Situ (DCIS) of the breast.

4.1.2 \_\_\_\_\_ Final pathologic Tis, T1-T3, all must be N0 and M0 status).

4.1.3 \_\_\_\_\_ Negative inked histologic margins from lumpectomy, with the exception of a focus of positive margin at the pectoralis fascia.

4.1.4 \_\_\_\_\_ Radiation oncologist does not plan to treat regional lymph nodes beyond standard whole breast tangent fields.

4.1.5 \_\_\_\_\_ Lumpectomy with negative lymph node on surgical evaluation (Isolated tumor cells in lymph nodes will be permitted). Patients with invasive carcinoma  $\geq 70$  yrs and with ER+ positive tumor  $\leq 2.0$ cm may enroll without surgical lymph node evaluation, per section 5.1. Patients with Ductal Carcinoma In Situ (DCIS) of the breast only may enroll without surgical lymph node evaluation.

4.1.6 \_\_\_\_\_ Negative serum or urine  $\beta$ -HCG in women of child-bearing potential  $\leq 7$  days prior to registration.

A female of childbearing potential is a sexually mature female who has not undergone a hysterectomy or bilateral oophorectomy and has not been naturally postmenopausal for at least 12 consecutive months.

4.1.7 \_\_\_\_\_ Women of child-bearing potential must agree to utilize a form of birth control or agree to undergo sexual abstinence during radiation therapy.

4.1.8 \_\_\_\_\_ ECOG (Zubrod) Performance Status 0-1.

4.1.9 \_\_\_\_\_ Patient  $\geq 18$  years of age.

4.1.10 \_\_\_\_\_ Able to provide informed consent and willing to sign an approved consent form that conforms to federal and institutional guidelines.

#### **4.2 Exclusion Criteria**

##### **Yes/No (Response of “yes” = patient ineligible)**

- 4.2.1  Prior radiation therapy to the chest, neck or axilla.
- 4.2.2  Prior history of ipsilateral breast cancer (invasive disease or DCIS). LCIS and benign breast disease is allowed.
- 4.2.3  History of prior or concurrent contralateral invasive breast cancer. Benign breast disease, LCIS or DCIS of contralateral breast is allowed.
- 4.2.4  Active collagen vascular diseases, such as: systemic lupus erythematosus, scleroderma, or dermatomyositis.
- 4.2.5  Significant post lumpectomy complications requiring an unplanned re-operation or admission for IV antibiotics. Re-operation for margins evaluation or nodal evaluation is acceptable.
- 4.2.6  Co-existing medical conditions with life expectancy < 5 years.
- 4.2.7  Other malignancy within 5 years of registration with the exception of basal cell or squamous cell carcinoma of the skin treated with local resection only or carcinoma in situ of the cervix.
- 4.2.8  Neoadjuvant chemotherapy or adjuvant chemotherapy delivered before radiation.
- 4.2.9  Neuroendocrine carcinoma or sarcoma histology.
- 4.2.10  Concurrent radiation sensitizing medications concurrent with radiation, per treatment physician.

## 5 TREATMENT PLAN

**Initial surgery** is defined as lumpectomy and any subsequent surgeries related to the initial lumpectomy, including additional margin resection, or lymph node removal.

**Radiation treatment** may begin no later than 84 days after initial surgery.

Chemotherapy must be delivered after (NOT BEFORE) radiation.

**Chemotherapy** is defined as cytotoxic chemotherapy, not biological therapy, such as trastuzumab, pertuzumab, etc.

### 5.1 Surgical Management

#### Lumpectomy

Margins should be negative, defined as no tumor on ink. A focally positive deep margin will be considered a negative margin if the deep margin is the pectoralis fascia. This is provided there is no evidence of pectoralis fascia invasion by imaging or pathological evaluation.

Lymph nodes must be evaluated by sentinel node biopsy or axillary dissection. The exception, per the CALGB 9343 criteria is patients who are  $\geq$  age 70 and have ER positive tumors  $\leq$  2.0cm. These patients will not require lymph node evaluation. This protocol does not stipulate sentinel node versus axillary dissection, but does require lymph node management per standard of care. Patients will be recorded as having undergone a sentinel node only procedure or an axillary dissection. A sentinel node procedure will be considered an axillary dissection if more than 5 lymph nodes are removed.

### 5.2 Systemic Therapy

Any **adjuvant hormonal therapy** is allowed. It may begin any time relative to the radiation, at the discretion of the treating physician.

**Chemotherapy** is allowed, but must be delivered after radiation therapy. Neoadjuvant chemotherapy is not allowed. Patients may be co-enrolled on systemic therapy trials, if there is no contraindication on the other trial.

Cytotoxic systemic therapy may not be used concurrently with radiation; however, trastuzumab, pertuzumab or other biological therapy may be given concurrently per standard of care.

If cytotoxic chemotherapy is started after radiation, a minimum of 10 days must pass after the last fraction of radiation before beginning chemotherapy. If a patient is experiencing a CTCAE Grade 2 or higher skin reaction, it is recommended that this be extended to 21 days, or until the skin reaction has resolved.

Protocol name: NOVEMBER (Novem- (9), BrEast Radiation), A Phase II trial of a 9 day course of whole breast radiotherapy for early stage breast cancer.

Version Date: 23NOV2021

Principal Investigator: [name]

### **5.3 Radiotherapy**

Radiation therapy treatment planning should begin after consultation with the radiation oncologist and prior to radiation treatment.

#### **5.3.1 Technical Factors**

3-dimentional CT based treatment planning is required. Megavoltage photon beam energies with energies  $\geq$  4 MV are required. Electron beams require megavoltage energies, if utilized. Proton beams are not allowed on this trial.

#### **Localization, simulation and immobilization**

Simulation and treatment must be performed with the patient in the supine or prone position. Patients should be optimally positioned with alpha cradle casts, vac fix, breast boards, wing boards and/or other methods of immobilization at the discretion of the treating physician.

Methods to minimize the cardiac exposure to RT such as a heart block, gating or breath-hold are allowed at the discretion of the treating physician.

A treatment planning CT scan in the treatment position will be required to define the clinical target volumes (CTV), planning target volumes (PTV), and Organs at Risk (OAR).

Radio-opaque markers are to be placed on the patient's skin in the treatment position as external landmarks at the acquisition of the CT scan to facilitate contouring segmentation of the CT data-set.

The CT scan should extend cephalad to start at or above the mandible and extend sufficiently caudally (or inferiorly) to the inframammary fold to encompass the entire lung volume. A CT scan image thickness of  $< 0.5$  cm should be employed.

External skin localizing marks, which may include permanent tattoos, are recommended for radiation daily localization and set-up accuracy.

Use of IMRT is allowed. Please see the section below for IMRT guidelines.

Calculations shall take into account the effect of tissue heterogeneities.

